**Synopsis**

Device Names	Pivot Breath Sensor
Protocol Title	Pivot Breath Sensor Human Factors and Usability Study [REDACTED]
Principal Investigators	[REDACTED]
Co-Investigators	[REDACTED]
Protocol Number	[REDACTED]
Protocol Version	[REDACTED]
Sponsor	Carrot Inc. [REDACTED]
Study Design	Prospective, observational open label, single center study enrolling up to 15 subjects to evaluate human factors and usability of the Pivot Breath Sensor. No medical decisions will be made related to test results.
Primary Objective	
Human Factors and Usability:
 
 
• Ensure that intended users are able to operate the Pivot Breath Sensor independently
 
• Validate appropriate mitigations of use related hazards identified in risk management documentation.
 
• Uncover previously unforeseen use errors.
 

Potential Subjects	
 
• Up to 15 subjects who self-report smoking 2 or more cigarettes each day.
 

Inclusion Criteria	
 
• 18-80 years of age
 
• English speaking
 
• Owns and uses a smartphone
 
• Willing to sign the Informed Consent Form
 

Exclusion Criteria	
 
• Prior experience with a study sponsored by Carrot Inc
 
• Pregnancy
 

Recruitment	Eligible subjects will be identified via a clinical research recruiter and/or advertisement at outdoor locations (i.e. flea markets, outside of movie theaters, shopping malls, train stations, stores that sell cigarettes), print media (i.e., local newspapers, billboards), and web media (i.e., Craigslist, Facebook).
Study Session	Single day study including: observation of user set up and use of the Pivot Breath Sensor, user documentation assessment, subjective feedback and rating scales.
Human Factors and Usability Outcomes	Assessment of intended user performance in use scenarios, user documentation assessment, subjective feedback and rating scales.

## 1. LIST OF ABBREVIATIONS

CO	Carbon Monoxide
CRF	Case Report Form
USB	Universal Serial Bus
IRB	Institutional Review Board
ICF	Informed Consent Form
ppm	parts per million
QSG	Quick Start Guide
UM	User Manual

## 2. INTRODUCTION

## 2.1 BACKGROUND

Smoking tobacco products is a leading cause of preventable morbidity and mortality, excess health care expenditure, and lost work productivity. [REDACTED]

Since our 2018 study, Carrot Inc. (Redwood City, CA, USA) has made improvements to the CO breath sensor (the Pivot Breath Sensor). The Pivot Breath Sensor consists of a stand-alone handheld breath sensor to measure CO in exhaled breath with a display screen to show results. This breath sensor can optionally be used with a smartphone app (Pivot Application). The Pivot Breath Sensor is intended to be used as a personal and mobile product and to be available 'over the counter'.

This study will assess the human factors and the usability of the Pivot Breath Sensor.

## **2.2 STUDY RATIONALE**

We aim to assess whether an untrained lay user group (representative of intended users) can operate the device and interpret the results correctly using only the instructions that will be provided with the marketed device.

## **2.3 POTENTIAL RISKS AND BENEFITS**

### **2.3.1 Known Potential Risks**

There are no anticipated risks or harms to the subject. No medical decisions are made based on study data.

### **2.3.2 Known Potential Benefits**

While we do not anticipate that subjects will receive any benefit from their participation in this study, it is possible that some subjects may experience an increased awareness of their smoking behavior.

### 2.3.3 Risk Benefit Assessment

Given the non-invasive nature of the breath sampling and the data collection, there are no anticipated risks to subject safety. Study staff will be with subjects and monitoring their use of the study devices for the duration of the study. Subjects are not asked to change their smoking behavior. No medical decisions are made based on study data.

## 3. OBJECTIVES

The objectives of the study are to:

- Ensure that representative intended users are able to operate the Pivot Breath Sensor independently, focusing on the following:
  - Proper breath sample collection
  - User comprehension of how to navigate the Pivot Breath Sensor screen
  - User interpretation and comprehension of their results
- Validate appropriate mitigations of use related hazards identified in risk management documentation
- Uncover previously unforeseen use errors

Overall, this human factors and usability testing is conducted to demonstrate that the Pivot Breath Sensor can be used by the intended users without serious use errors or problems, for the intended uses and under the expected use conditions.

## 5. DEFINITIONS

Close Call (a.k.a. “Near-Miss”): Instances in which a user has difficulty or makes a use error that could result in harm, but the user takes an action to “recover” and prevents the harm from occurring (FDA Guidance 2016).

Critical Task: A user task which, if performed incorrectly or not performed at all, would or could cause serious harm to the patient, user, or instrument, where harm is defined to include compromised medical care.

Objective Data: Data collected through direct observation.

Pivot Breath Sensor: The study device. It is a personal mobile breath sensor that is capable of measuring the level of carbon monoxide (CO) in exhaled breath. It is portable, battery-

powered, and small enough to be carried by the user throughout the day (pocket, purse, backpack). The sensor is intended for single-user use by cigarette smokers to inform the user about how breath carbon monoxide levels are affected by smoking behavior. The user submits a breath sample by exhaling (blowing) directly into the mouthpiece connected to the sensor.

Subjective Data: Data collected through user feedback via comments, ratings, and assessments provided by participants.

Task: Action or set of actions performed by a user to achieve a specific goal.

Use Error: User action or lack of action that was different from that expected by the manufacturer and caused a result that (1) was different from the result expected by the user and (2) was not caused solely by device failure and (3) did or could result in harm. (Section 3.9, FDA Guidance 2016).

User: Person who interacts with (i.e., operates or handles) the Pivot Breath Sensor.

## 6. PIVOT BREATH SENSOR, STUDY DEVICE

The Pivot Breath Sensor comprises a personal mobile breath sensor that measures the level of CO in exhaled breath and displays the exhaled breath CO value to the user directly on the device. The range of CO measurement is 0-100 ppm.

The Pivot Breath Sensor (Figure 1) is portable, battery-powered, and small enough to be conveniently carried by the user throughout the day (pocket, purse, backpack). The Pivot Breath Sensor is rechargeable using a micro-USB cable. The user submits a breath sample by exhaling (blowing) into the mouthpiece of the Pivot Breath Sensor.

### 6.1 INDICATIONS FOR USE

*The Pivot Breath Sensor is a breath carbon monoxide monitor intended for single-user use by cigarette smokers to inform the user about how breath carbon monoxide levels are affected by smoking behavior. The device is not intended to be used with other inhaled products.*

**Figure 1. Pivot Breath Sensor**

### 6.2 LABELING AND PACKAGING

The Pivot Breath Sensor package includes:

- 1 Pivot Breath Sensor
- 1 USB charging cable
- 1 Replaceable Mouthpiece
- 1 Quick Start Guide [REDACTED]

The Pivot Breath Sensor packaging is shown in [REDACTED]

### **6.3 SUBMITTING A BREATH SAMPLE (SPECIFIC STEPS)**

Submitting a breath sample involves the following steps. Instructions can be accessed in multiple locations including the Pivot Sensor's display screen, the Quick Start Guide, on the packaging or also in the User Manual that will be available online.

1. User presses any button to turn on the Pivot Breath Sensor.
2. User presses and holds the center button on the Pivot Breath Sensor until the sensor beeps once.
3. User takes a deep breath in and holds their breath for 10 seconds.
4. After about 10 seconds, the device beeps 3 times, the user then will exhale slowly until the sensor vibrates at 12 seconds.
5. The user's CO level will display on the sensor's screen.

A properly submitted breath sample is defined as one that initiates after the third beep prompt and is of at least 6 seconds duration. Breath sensor hardware and firmware is capable of detecting when a breath sample submission starts and stops.

The CO Log screen in the Pivot Breath Sensor provides the CO (ppm) value for properly submitted breath samples and provides a descriptive error message for improperly submitted breath samples (i.e. "Error: breath sample too late").

The computation of concentration of CO (ppm) is performed within the Pivot Breath Sensor firmware and the data (CO ppm concentration, time and date) are stored in the Pivot Breath Sensor memory.

### **6.4 CO LOG**

The CO Log can be accessed from the Pivot Breath Sensor's display screen and shows the most recent exhaled breath CO value in ppm at the top of the screen. The user can view previous values by scrolling within the log (Figure 2).

Values are color coded and can be interpreted by the user with help from the labeling (Figure 3).

**Figure 2. CO log on Pivot Breath Sensor****Figure 3. Package labeling to interpret results**

## How to interpret your CO sample

Remember: no amount of smoking is safe

Each of your breath sample results is displayed on the sensor screen with a color and a number and are measured in parts per million (ppm).

**0–6 ppm**

Typical levels for a non-smoker, and should be your goal.

It is normal to have some CO in your body.

**7–9 ppm**

Borderline values that may be found in smokers and non-smokers.

**10+ ppm**

[figure not shown]
Typical levels for a smoker.

If you are a smoker, you may also obtain a green or orange reading if you have not smoked for an extended period of time.

## 7. TASK ANALYSIS AND IDENTIFICATION OF CRITICAL TASKS

For the human factors and usability portion of the study, a task analysis was performed to identify the tasks associated with the use of the Pivot Breath Sensor. The task analysis is depicted in Figure 4.

**Figure 4. Task Analysis of Pivot Breath Sensor**  
(Note: Sub-work flow is shown in lighter blue.)

As part of the product development process, a comprehensive use related failure mode and effect analysis (Use FMEA) was performed to identify and analyze the potential use-related failure modes (i.e., use errors) that might occur when the intended users interact with the Pivot Breath Sensor.

The task analysis and the Pivot Breath Sensor Use FMEA were assessed for critical tasks. Based on the definition of a critical task provided in FDA “Guidance for Industry and Food and Drug Administration Staff: Applying Human Factors and Usability Engineering to Medical Devices,” issued on February 3, 2016 (“A user task which, if performed incorrectly or not performed at all, would or could cause serious harm to the patient or user, where harm is defined to include compromised medical care”), it was identified that the Pivot Breath Sensor does not have use related tasks that may result in serious harm or compromised medical care if the device is not operated properly by the user. [REDACTED]

[REDACTED] Carrot Inc. chose to perform usability testing to assess user tasks and comprehension items that are essential to the effective operation of the device and user interpretation of breath sample results, and, to monitor for unforeseen use errors that could lead to serious harm.

**Table 1. List of “Severity 2” Tasks**

User Tasks and Comprehension Items	Severity
[REDACTED]	[REDACTED]

## 8. STUDY DESIGN AND OVERVIEW

### 8.1 STUDY DESIGN

This is a prospective open-label human factors and usability study, conducted with IRB approval, enrolling up to 15 subjects who report daily smoking. The study will be conducted at our research center in Redwood City, CA or an equivalent location. Subjects will be asked to set up the Pivot Breath Sensor and provide a breath sample using the device during a 60-minute session. No follow-up visit is required.

### 8.2 STUDY ENDPOINTS

Assessment of intended user performance in use scenarios, user documentation assessment, subjective feedback, and rating scales.

### 8.3 ELIGIBILITY CRITERIA

The intended user population (user group) for the Pivot Breath Sensor System are lay users who are smokers, ages 18-80, capable of using a smartphone to track/monitor health-related data. The intended users range in age, degree of smoking, mental and physical

capabilities, health literacy, experience using other CO analyzers or home use medical devices, and experience using smartphones.

Study participants will consist of individuals who represent the intended user profile, current smokers. Participant criteria include all of the following:

#### Inclusion Criteria

- 18-80 years of age
- Current daily cigarette smokers (at least 2 cigarettes per day with target distribution of individuals who smoke: 2-5 cigarettes per day, 6-10 cigarettes per day, 11-15 cigarettes per day and 16+ cigarettes per day)
- Resident of the United States
- Able to read and comprehend English
- Currently own and use an Apple, Inc. iPhone iOS smartphone or an Android smartphone for at least one month (such that they are familiar with basic operations of the mobile platform)
- Willing to sign the Informed Consent Form

#### Exclusion Criteria

- Prior experience with a study sponsored by Carrot Inc.
- Pregnancy

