## 10. DATA COLLECTION

Study personnel will collect information about the participant including

- Age
- Gender
- Race/ethnicity
- Vision
  - Wear glasses?
  - Color blind?
- Hearing
  - Hearing issues?
  - Use a hearing aid?
- Type of smartphone participant uses (iPhone or Android)
- Number of years smoking
- Number of quit attempts over the past 12 months
- Number of cigarettes currently smoked per day

- Smoking history in the past 24 hours
  - Number of cigarettes smoked
  - Time of last cigarette
  - Use of any combustible, inhaled tobacco product other than cigarettes (pipes, cigars, cigarillos, etc.), any electronic cigarette product (e-cigs, vape, vapor), and any other inhaled combustible material
- Attitudes towards smoking
  - Desire to quit
  - Readiness to quit
  - Confidence to quit
  - Perceived difficulty of staying quit
- Current smoking cessation medications
- Participation in a smoking cessation program
  - Past
  - Present
- Breath sensor use (past)
  - Use of CO breath sensors in the past
- Breath sensor use during the study session
  - Model#/Lot# of breath sensor
  - CO measurements

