### 13. CONFLICTS OF INTEREST

The following conflicts of interest are noted:

- The study sponsor is Carrot Inc. [REDACTED]
- The investigator owns equity in Carrot Inc., which is the company that invented and owns two of the breath sensors being evaluated in this study.
- The company (Carrot Inc.) holds patent rights to two of the devices being evaluated in the study (the Pivot Breath Sensor and the CO Breath Sensor).

The investigators hold the following positions:

- [REDACTED] Sr. Director of Clinical and Medical Affairs (senior management officer)
- [REDACTED] Director, Clinical Affairs
- [REDACTED] Senior Clinical Research Associate, Clinical Affairs

These conflicts of interest are mitigated by the following:

- The risk profile of the study, specifically, that there are no anticipated risks or harms to the subject. No medical decisions are made based on study data. The process of

setting up the Pivot Breath Sensor and providing breath samples is non-invasive, and done under the guidance of trained study personnel. Study participants will be able to indicate how they are feeling and if they would like to continue or discontinue giving breath samples.

- The role of Carrot Inc. in the study is outlined in the study Informed Consent Form; participants will be aware of this role prior to providing informed consent.
- The aim of the study is to assess the usability of the Pivot Breath Sensor in intended users and then use this data to optimize the product as needed. This study will inform resultant improvements made to the Carrot Inc. products (the Pivot Breath Sensor). As such, it is imperative, and the goal, that the study sponsor uses this data to ensure its products are as user-friendly and accurate as possible.

14. [REDACTED]

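### The prior-exposure exclusion is keyed to sponsor-study participation, so it does not cover earlier use of the sponsor's sensor outside a study or sponsor employment

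*Combined protocol and SAP*

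**What the plan says.** - **Exclusions.** The synopsis and Section 8.3 list two: "Prior experience with a study sponsored by Carrot Inc" and pregnancy. Neither mentions use of the device.
- **Aim.** Section 2.2: "We aim to assess whether an untrained lay user group (representative of intended users) can operate the device", relying only on the instructions to be supplied with the marketed product.
- **Intended users.** Section 8.3 describes them as "lay users who are smokers, ages 18-80, capable of using a smartphone to track/monitor health-related data". Among the ways they may vary it names "capabilities, health literacy, experience using other CO analyzers or home use medical devices, and experience using smartphones". It adds that participants will match this profile.
- **How eligibility is applied.** Section 8.4 offers participation, after a screening call, to people who meet the listed inclusion and exclusion criteria.
- **Past use.** Section 10 collects "Use of CO breath sensors in the past". The item names no maker, and neither Section 12.2.1 (analysis) nor Section 12.3 (report) says what will be done with it.
- **Other sponsor devices.** Section 13 names two sponsor devices, "the Pivot Breath Sensor and the CO Breath Sensor". The footnote on sample size describes earlier usability testing of a similar predecessor.
- **Acceptance.** Section 11.1 sets no task-specific criterion. Observed hazard-related scenarios are judged for risk acceptability under the Use FMEA.

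**The concern.** Use Scenario 2 (Section 11.3.2) stages a first encounter: the participant is handed an unused sensor and asked to behave as a new purchaser would at home. The result is informative only if the participant has to learn the device from its labeling and screen. Someone who already knows the timed hold-and-exhale sequence in Section 6.3, or the color bands in Section 6.4, does not test whether the materials teach them.

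The exclusion appears to be aimed at this problem, but it screens on where the exposure happened rather than on whether it happened. A person who had used a sponsor sensor outside a study would meet every listed criterion, and so would a sponsor employee who smokes.

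The effect runs mainly one way. Familiar users should make fewer errors, and under Section 11.1 an error that is not observed has nothing to trigger its assessment. The conclusion about untrained users would then be somewhat too favorable.

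**Working it through.** **1. Is there a figure to reproduce?** No. Section 8.6 takes its 15 participants from cited guidance, with no assumed error rate, power or margin. The calculation below only gives scale.

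**2. Which exposures do the listed criteria catch?**

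| Earlier exposure | Listed criteria | Consistent with the aim? |
|---|---|---|
| Took part in a sponsor study | Excluded | Yes |
| Used or was taught a sponsor sensor outside a study | Eligible | No |
| Current or former sponsor employee | Eligible | No |
| Used another maker's CO analyzer | Eligible | Yes, by design (Section 8.3) |

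The middle two rows are the gap.

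**3. Effect on error detection.** Inputs: n = 15 (Section 8.6). Assumed, because the documents give no values: p, the chance that a naive user makes a given error (5%, 10% or 20%), and k, the number of participants who would never make it because they know the device (0 to 3). With n − k naive users,

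P(error seen at least once) = 1 − (1 − p)^(n − k)

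| p | k = 0 (15 naive) | k = 1 (14) | k = 2 (13) | k = 3 (12) |
|---|---|---|---|---|
| 5% | 53.7% | 51.2% | 48.7% | 46.0% |
| 10% | 79.4% | 77.1% | 74.6% | 71.8% |
| 20% | 96.5% | 95.6% | 94.5% | 93.1% |

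The first familiar participant costs p(1 − p)^14:
- p = 5%: 53.7 − 51.2 = 2.5 points (2.4 before rounding)
- p = 10%: 79.4 − 77.1 = 2.3 points
- p = 20%: 96.5 − 95.6 = 0.9 points

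The third costs 48.7 − 46.0 = 2.7, 74.6 − 71.8 = 2.8 and 94.5 − 93.1 = 1.4 points. So each of the first three costs about 1 to 3 points.

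**4. If no error is seen.** The one-sided 95% upper bound on the naive-user error rate is 1 − 0.05^(1/m) for m naive users. It is 18.1% at m = 15 and 22.1% at m = 12.

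**5. Could the data show the problem afterwards?** Only in part. The Section 10 item would identify anyone with past CO-sensor use. As worded, it cannot separate a sponsor-sensor user from a user of another brand.

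**The case against.** The best defense is that the exclusion fits the only exposure route the documents describe. Section 2.2 speaks of the marketed device in the future tense, and Section 2.1 says it is intended to be available over the counter, so it reads as not yet on sale. Nothing says that the predecessor could be had outside studies. The one described exposure is the earlier usability testing, which the exclusion covers if the sponsor ran it. Untrained can also fairly be read, with Section 8.9, as having had no in-person training, rather than having no experience of any kind. All of this stands, and it limits the practical reach of the point. It does not make study participation a measure of device use.

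Stronger readings are tempting, but the documents do not support them:

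- **Non-lay users are admitted.** A reader might infer this because no listed criterion says lay. But Section 8.3 states "The intended user population (user group) for the Pivot Breath Sensor System are lay users who are smokers" and requires participants to fit that profile. It also allows varied health literacy and experience with other analyzers. A smoking nurse who buys the device for personal use is arguably an intended user, so barring all health-care or cessation professionals is a debatable trade-off.
- **Recruiting near the sponsor's office draws in insiders or their households.** Section 8.4 lists broad public channels, and Section 8.10.1 allows rented space nearer to participants. Nothing points to such a concentration.
- **A fixed share of the evidence is lost.** One to three of 15 is 1/15 = 6.7% to 3/15 = 20%, but that count is invented, and the study has no success-rate threshold for such a share to distort.

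**Conclusion.** The point holds as a wording gap with a predictable direction. The exclusion uses a proxy that does not cover use of a sponsor sensor outside a study or sponsor employment, while the aim concerns people who learn the device from its own materials.

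Its size is modest: about 1 to 3 percentage points of detection probability per familiar participant. This assumes naive-user error rates of 5% to 20% and familiar users who never make the error. If they sometimes do, the loss is smaller. The number of such participants is unknown and may be zero.

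A reader should not infer that experienced users will be enrolled, that users of other makers' analyzers are a defect, or that the sample size must change. This is a cheap improvement.

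**What to change.** 1. In Section 8.3 and the synopsis, extend the exclusion to read: *prior participation in a Carrot Inc. study, any prior use of or instruction on a Carrot Inc. breath sensor (Pivot Breath Sensor or CO Breath Sensor), or current or former Carrot Inc. employment.* Ask about each on the existing screening call.
2. Keep users of other makers' CO analyzers eligible, as Section 8.3 intends.
3. Have the Section 10 past-use item record the maker.
4. In Sections 12.2.1 and 12.3, state that task ratings will be listed by past CO-sensor use. With 15 participants this is a listing, not a comparison.

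Cost: a few screening questions, one added field and one column in the results table. The downside is a slightly smaller recruitment pool.
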